## **Research questions**

- Does the Close Collaboration with Parents training program affect the length of stay in neonatal units?
- Does single-family room architecture affect the length of stay in neonatal units?
- Do the interventions affect the need for outpatient visits after discharge during the first year of life?
- Are the interventions cost-effective?
- Do the interventions affect early postnatal growth in preterm infants?

[figure not shown]
Our hypotheses are that the length of stay will be shorter, outpatient visits fewer and early postnatal growth better in units where either or both of these interventions have been implemented.

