## **Methods**

The study population will consist of all newborn infants born from January 1st 2006 to December 31st 2020, who have needed care in a neonatal unit immediately after birth. These infants will be identified from the Hospital Discharge Register. Data on vital background data, birth details, diagnoses, length of stay, growth parameters and outpatient visits will be obtained from the Hospital Discharge Register and the Medical Birth Register. These data will be linked through the infants' personal identification codes, which will be replaced by a pseudonymized ID-number before delivering the data to the research group. Planned subgroup analyses will be done for preterm infants and for infants with significant congenital anomalies.

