### Outcomes:

The *primary* outcome is the length of stay during the initial hospitalization to neonatal care. Comparisons will be made between infants cared for in intervention units and those cared for in non-intervention units.

*Secondary* outcomes are:

Corrected gestational age at discharge

The amount of outpatient visits after discharge during the first year of life

Growth parameters (weight, length, head circumference) at discharge compared to national standards

Change in growth parameters from birth to discharge

Cost effectiveness (according to hospitalization cost analyses carried out by the Institute for Health and Welfare)

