### Statistical analysis:

The planned analyses include a linear mixed model-approach to account for the effect of unit, degree of prematurity and intervention. Variables that will be considered for inclusion into the model are gestational age at birth, mode of delivery, birth weight z-score, plurality, neonatal morbidities, and receipt of antenatal steroids.

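### The candidate covariate for neonatal morbidities is not limited to conditions present at birth or admission, so the primary model may not estimate the overall effect on length of stay

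*Combined protocol and SAP*

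**What the plan says.** The Statistical analysis section plans a linear mixed model accounting for unit, degree of prematurity and intervention. It then introduces a candidate list with the words "Variables that will be considered for inclusion into the model". Two of the six entries are mode of delivery and gestational age; the other four read "birth weight z-score, plurality, neonatal morbidities, and receipt of antenatal steroids". It gives no selection rule, no list of morbidities and no limit on their time of onset.

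The Methods section names the Medical Birth Register and the Hospital Discharge Register as the sources and describes what they supply: "Data on vital background data, birth details, diagnoses, length of stay, growth parameters and outpatient visits will be obtained". It does not say which diagnoses are meant as covariates, or whether onset is dated. The population is infants "who have needed care in a neonatal unit immediately after birth", and one planned subgroup analysis is "for infants with significant congenital anomalies".

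The primary outcome is "length of stay during the initial hospitalization to neonatal care". The research questions put the aim in two parallel forms. For the training program the wording is "Does the Close Collaboration with Parents training program affect the length of stay in neonatal units"; for the change of building it is "Does single-family room architecture affect the length of stay in neonatal units". Neither asks for an effect apart from some pathway, and no mediation analysis is described anywhere.

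**The concern.** Neonatal morbidities can mean two different things. Some are present at birth or admission and describe the infant's case-mix. Others develop in the unit and may partly result from the care given there. Adjusting for the first kind is ordinary confounding control in a comparison of non-randomised units. Adjusting for the second kind holds fixed something that follows exposure, and if an intervention changes it, that part of the effect on stay is taken out of the intervention coefficient.

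What is at stake is the meaning of the primary estimate. With timing unstated, a reader could not tell whether the reported number of days is the overall effect or an effect conditional on how the stay went. With no selection rule, that choice could also be settled after the data have been seen.

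**Working it through.** The plan gives no sample size, standard deviation, target effect or morbidity rate, so there is no figure of its own to reproduce. The check is of timing first, then of the statistical consequence.

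**Step 1: when each candidate is determined.**

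| Candidate (Statistical analysis) | Determined |
|---|---|
| Gestational age at birth | by birth |
| Mode of delivery | by birth |
| Birth weight z-score | by birth |
| Plurality | by birth |
| Antenatal steroids | by birth |
| Neonatal morbidities | not stated; could be before or after admission |

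**Step 2: when exposure and outcome run.** Methods places entry to the unit immediately after birth. Outcomes defines the primary outcome as the length of that initial stay. Exposure to the care model and the outcome therefore run together from admission, and any condition first arising in the stay follows the start of exposure. The register diagnoses, if used without restriction, could mix both kinds.

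**Step 3: the consequence.** In a linear model,

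overall effect = direct effect + (days per case × change in in-stay morbidity risk).

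With no unmeasured common cause of morbidity and stay, a model that also contains the in-stay morbidity returns only the first term.

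**Step 4: illustration with unit effects.** Every input is assumed; none is in the documents. There are 20 units with before/after exposure coding and fixed unit effects, a direct effect of −2 days and 20 days per case. Unmeasured severity raises both morbidity and stay, and differs between units by a constant 0.25 SD. Paired figures are for the two directions of that difference.

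| Assumed change in in-stay morbidity | Overall effect (days) | Model without in-stay morbidity | Model with it |
|---|---|---|---|
| 5-point drop | −2 + 20 × (−0.05) = −3.0 | −2.93, −3.03 | −1.89, −1.98 |
| 2-point drop | −2 + 20 × (−0.02) = −2.4 | −2.39, −2.44 | −1.97, −1.95 |
| None | −2 + 20 × 0 = −2.0 | within 0.1 of −2.0 | within 0.1 of −2.0 |

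For the 5-point drop, the model without in-stay morbidity misses the overall effect by 0.07 and 0.03 days (3.0 − 2.93; 3.03 − 3.0). The model with it misses by 1.11 and 1.02 days (3.0 − 1.89; 3.0 − 1.98). A separate run with unit effects gave about −3.1 and −1.9 for a true −3.0. The figure of −1.89 also differs from the assumed direct effect of −2: with unmeasured severity, the model with in-stay morbidity need not return the direct effect cleanly either.

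**Step 5: where the illustration stops.** When the severity shift was made to coincide with the intervention, both models were biased, and the one with in-stay morbidity was the closer in most cases. The documents do not say whether unit effects are fixed or random, or how exposure is timed, so Step 4 shows the mechanism and does not forecast this study's result.

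**The case against.** The strongest reply is that the plan has committed no error. The covariate is only under consideration, and harm needs three things together: in-stay conditions are meant, they are selected, and an intervention changes them. The documents do not establish the third. The hypotheses concern stay, visits and growth, and no morbidity outcome is listed. The Background reports better weight gain and earlier breastfeeding after the training program, but no change in morbidity. The title of the cited randomised single-family-room study (reference 15) names infant morbidity, but its morbidity result is not given. This stands, and it is why no size can be claimed.

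The second reply is case-mix. Units were not randomised, and in-stay morbidity may be a useful proxy for severity that no birth variable captures. This stands in part. The planned unit effect can absorb constant severity differences between units, but not a shift that coincides with the intervention. In that situation neither model is always the closer one.

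The third reply is practical: the documents do not say that the registers date onset, so separating admission conditions from complications may be imperfect. That is true and is a cost of the remedy.

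The reply that an open choice is harmless does not stand. Following the section as written permits a primary model that answers a different question from the one posed.

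**Conclusion.** The point holds in conditional form. One of six candidates is not limited to conditions fixed by birth or admission, and nothing elsewhere in the document limits it. If in-stay conditions are included and an intervention changes them, the primary model does not estimate the overall effect on length of stay. The size cannot be computed from the documents and may be zero. The change should be made before analysis, but the point does not show that any result will be wrong.

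A reader might infer more, and the documents do not support it:

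- That the plan will adjust for complications of the stay. It lists candidates only.
- That the primary estimate will be pulled towards no effect. That would need an intervention that lowers both morbidity and stay, and neither document section nor cited result shows a change in morbidity.
- That adjustment is harmless whenever morbidity is unchanged. That fails if unmeasured severity shifts with the intervention.
- That the model without in-stay morbidity is always less biased. The reason to make it primary is that it targets the question asked.
- That the growth and outpatient-visit models share the problem. The documents do not say that they use this covariate list.

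**What to change.** In the Statistical analysis section, limit the primary length-of-stay model to covariates fixed at or before birth or admission, alongside the planned unit effect: gestational age, birth weight z-score, plurality, mode of delivery, antenatal steroids, congenital anomalies, and conditions present at admission. Before analysis, list which register diagnoses count as admission conditions and which as in-stay conditions, sorting by type of diagnosis where onset is not dated. Report beside the primary model a labelled sensitivity model that adds the in-stay morbidities. State that a gap between the two is not proof that an intervention acts through morbidity, because a difference in unmeasured severity can also produce one.

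The cost is a few lines of text and a diagnosis list. The diagnoses are already requested, and congenital anomalies must be identified anyway for the planned subgroup. The downsides are slightly less precision in the primary model, some misclassified diagnoses, and residual confounding if severity shifts at the same time as an intervention. Because of that last risk, both models should be shown.

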### Timeline

During the year 2020 the research group has applied for funding, and research data permit from the Institute for Health and Welfare. Processing of the pseudonymized data will be initiated during the autumn of 2021. The analyses of the data and calculating of cost effectiveness will be done during 2021-2022. The manuscripts for scientific publishing will be drafted and submitted for publication during 2022-2023.

## **Meaning and potential implications**

Costly interventions are done in neonatal care to enable parental involvement. The effects of these interventions are important for future resource allocation, so that investments can be planned based on scientific evidence. Also other fields of medicine nationally and internationally, both in pediatrics and adult medicine, could benefit from interventions that advance care practices and family centered care culture.

